**Table 3 CDR Computerized Assessment System Variables**

Task Name	Variable	Abbreviation	Unit
Immediate Word Recall	Words Recalled Correctly	IRCL	#
	Errors	IRCLERR	#
Simple Reaction Time	Mean Reaction Time	SRT	ms
	Median Reaction Time	SRTM	ms
	Standard Deviation	SRTSD	ms
Digit Vigilance	Mean Reaction Time	VIGRT	ms

Task Name	Variable	Abbreviation	Unit
	Accuracy	VIGACC	%
	False Alarms	VIGFA	#
	Standard Deviation	VIGSD	ms
Choice Reaction Time	Mean Reaction Time	CRT	ms
	Median Reaction Time	CRTM	ms
	Accuracy	CRTACC	%
	Standard Deviation	CRTSD	ms
Spatial Working Memory	Median Reaction Time	SPMRTM	ms
	Sensitivity Index	SPMSI	SI
Numeric Working Memory	Median Reaction Time	NWMRTM	ms
	Sensitivity Index	NWMSI	SI
Delayed Word Recall	Words Recalled Correctly	DRCL	#
	Errors	DRCLERR	#
Word Recognition	Median Reaction Time	DRECRMTM	ms
	Original Stimuli Accuracy	DRECOACC	%
	New Stimuli Accuracy	DRECNACC	%
Picture Recognition	Median Reaction Time	DPICRTM	ms
	Original Stimuli Accuracy	DPICOACC	%
	New Stimuli Accuracy	DPICNACC	%

**Table 4 Calculation of CDR Computerized Assessment System Domain Scores**

Name	Abbreviation	Unit	Calculation
Power of Attention	POW_ATT	ms	SRTM+VIGRT+CRTM
Continuity of Attention	CONT_ATT	#	(VIGACC*0.45)+(CRTACC*0.5)-VIGFA
Cognitive Reaction Time	COGRT	ms	CRTM-SRTM
Response Variability	POWATTCV	%	(SRTSD/SRT*100)+(CRTSD/CRT*100)+(VIGSD/VIGRT*100)
Quality of Working Memory	QL_WORK	SI	SPMSI+NWMSI
Quality of Episodic Secondary Memory	QL_EPIS	#	(DRECOACC+DRECNACC-100)+(DPICOACC+DPICNACC-100)+((IRCL-IRCLERR)*100/12)+((DRCL-DRCLERR)*100/12)
Speed of Memory	SPEEDMEM	ms	SPMRTM+NWMRTM+DRECRMTM+DPICRTM

Based on the derived domain scores, a standardized z-score will be derived for each CDR system domain using the formula below:

$$\text{Domain z-score} = (X_2 - X_1)/SD_1$$

Where:

$X_2$  is the domain score for each individual at any study assessment time post Baseline

$X_1$  is the Baseline domain score for that individual

$SD_1$  is the domain standard deviation of the population at Baseline

A composite z-score for the 7 CDR domains will be calculated based on the individual domain scores as:

(Continuity of Attention z-score + Quality of Episodic Secondary Memory z-score - Response Variability z-score + Quality of Working Memory z-score - Power of Attention z-score - Cognitive Reaction Time - Speed of Memory z-score)/7

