#### 4. OBJECTIVES AND ENDPOINTS

Objective	Endpoint
Primary Efficacy	

 
To assess the effects of RVT-101 versus placebo on motor function as measured by the Unified Parkinson's Disease Rating Scale – Part III (UPDRS-III) after 24 weeks of treatment
 
	Change from baseline in the UPDRS-III total score at Week 24
Secondary Efficacy	

 
To assess the effects of RVT-101 versus placebo on cognition as measured by the ADAS-Cog 11 after 24 weeks of treatment
 
	Change from Baseline on ADAS-Cog 11 at Week 24

 
To assess the effects of RVT-101 versus placebo on global function as measured by the CIBIC+ after 24 weeks of treatment
 
	Total score of the CIBIC+ at Week 24
Tertiary Efficacy	

 
To assess the effects of RVT-101 versus placebo on activities of daily living as measured by the ADCS-ADL scale after 24 weeks of treatment
 
	Change from Baseline in the ADCS-ADL at Week 24

 
To assess the effects of RVT-101 versus placebo on the Basic and Instrumental subscores of the ADCS-ADL scale after 24 weeks of treatment.
 
	Change from Baseline in the Basic and Instrumental subscores of the ADCS-ADL at Week 24

 
To assess the effects of Intepirdine versus placebo on the Unified Parkinson's Disease Rating Scale – Part III, 5-item subscale (UPDRS-5) after 24 weeks of treatment
 
	Change from baseline in the UPDRS-5 total score at Week 24

 
To assess the effects of RVT-101 versus placebo on cognition as measured by the composite z-score of the 7-domains of the CDR computerized assessment system after 24 weeks of treatment (CDR System domains include Power of Attention, Continuity of Attention, Quality of Working Memory, Quality of Episodic Memory, Speed of Memory, Cognitive Reaction Time and Reaction Time Variability)
 
	Change from Baseline in the composite z-score combining the 7 domains of the CDR computerized assessment system at Week 24

 
To assess the effects of RVT-101 versus placebo on working memory as a measure of executive function as assessed by the COWAT after 24 weeks of treatment
 
	Change from Baseline in COWAT score at Week 24

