
 
To assess the effects of RVT-101 versus placebo on cognitive function as measured by a composite z-score combining the 7 domains for the CDR computerized assessment system and the COWAT after 24 weeks of treatment
 
	Change from Baseline in composite z-score combining the 7 CDR System domains plus the COWAT at Week 24

 
To assess the effects of RVT-101 versus placebo on hallucinations and delusions as measured by a 2-item subscore on the NPI which is the sum of the scores for the hallucinations and delusions domains (Parts A and B) after 24 weeks of treatment
 
	Change from Baseline in the sum of Parts A and B of the NPI at Week 24

 
To assess the effects of RVT-101 versus placebo on visual hallucinations as measured by the NEVHI after 24 weeks of treatment
 
	Change from Baseline on the total severity score and distress score of the NEVHI score at Week 24 for subjects with visual hallucinations

 
To assess the effects of RVT-101 versus placebo on fluctuations in cognition using the CAF after 24 weeks of treatment
 
	Change from Baseline in CAF severity score at Week 24 for subjects with cognitive fluctuations

 
To assess the effects of RVT-101 versus placebo on subject dependence using the DS after 24 weeks of treatment
 
	Change from Baseline on DS at Week 24
Safety	

 
To assess the safety and tolerability of RVT-101 after 24 weeks of treatment
 
	AEs, physical examinations, vital signs (including orthostatic changes in BP and HR), ECGs, routine clinical laboratory assessments, questionnaire for symptoms potentially associated with orthostasis, and C-SSRS.
Exploratory	

 
To assess the effects of RVT-101 versus placebo on quality of life as measured by the EQ-5D-5L after 24 weeks of treatment
 
	Change from Baseline on EQ-5D-5L at Week 24

 
To assess the effects of RVT-101 versus placebo on sleep-related behaviors as measured by the modified CSI
 
	Change from Baseline on CSI scores (Part I, Part II) at Week 24

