**Table 13: Calculation of CDR Computerized Assessment System Domain Scores (Study RVT-101-2001)**

Name	Abbreviation	Unit	Calculation	Interpretation
Power of Attention	POW-ATT	ms	SRTM+VIGRT+CRTM	Lower scores are better
Continuity of Attention	CONT-ATT	#	(VIGACC*0.45)+(CRTACC*0.5)-VIGFA	Higher scores are better
Cognitive Reaction Time	COGRT	ms	CRTM-SRTM	Lower scores are better
Response Variability	POWATTCV	%	(SRTSD/SRT*100)+(CRTSD/CRT*100)+(VIGSD/VIGRT*100)	Lower scores are better
Quality of Working Memory	QL-WORK	SI	SPMSI+NWMSI	Higher scores are better
Quality of Episodic Secondary Memory	QL-EPIS	#	(DRECOACC+DRECNACC-100)+(DPICOACC+DPICNACC-100)+((IRCL-IRCLERR)*100/12)+ ((DRCL-DRCLERR)*100/12)	Higher scores are better
Speed of Memory	SPEEDMEM	ms	SPMRTM+NWMRTM+DRECRTM+DPICRTM	Lower scores are better

Based on the derived domain scores, a standardized z-score will be derived for each CDR system domain using the formula below:

$$\text{Domain z-score} = (X2 - X1)/SD1$$

Where:

X2 is the domain score for each individual at any study assessment time post Baseline

X1 is the Baseline domain score for that individual

SD1 is the domain standard deviation of the population at Baseline

A composite z-score for the 7 CDR domains will be calculated based on the individual domain scores as:

$$(\text{Continuity of Attention z-score} + \text{Quality of Episodic Secondary Memory z-score} - \text{Response Variability z-score} + \text{Quality of Working Memory z-score} - \text{Power of Attention z-score} - \text{Cognitive Reaction Time} - \text{Speed of Memory z-score})/7$$

Missing data will be handled as follows:

- If any individual item (variable) is missing for a Domain Score, the Domain Score will be set to missing. Thus, no imputation of individual Domain Scores will be performed; all variables are needed in order to calculate each Domain Score.
- If a single Domain Score is missing for the derivation of the Composite score (ie, one of the 7 Domain Scores is missing), the average of the 6 non-missing Domain z-scores will be used to replace the missing Domain z-score.
- If >1 Domain Scores are missing, the Composite score will be set to missing.

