#### 9.4.2. Tertiary Endpoints

Tertiary efficacy endpoints include the following. Note that analysis will be performed for each protocol-scheduled time point for each analysis variable and method, but the focus will be on the Week 24 time point.

- Change from Baseline on UPDRS-5 at Week 24
  - MMRM on observed data (also on UPDRS subgroups)
  - Wilcoxon Rank test on observed data
- Change from Baseline on ADAS-Cog 13 at Week 24
  - MMRM on observed data
  - Wilcoxon Rank test on observed data
- Change from Baseline in the Total score, and the Basic, Instrumental, Independence subscores of the ADCS-ADL scale at Week 24
  - MMRM on observed data (also on Concomitant Parkinsonian Meds subgroups)
  - Wilcoxon Rank test on observed data
- Change from Baseline in the Total Composite z-score and in the actual score (NOT the z-scores) of each individual domain of the CDR computerized assessment system at Week 24. Thus, in addition to the Total Composite, this includes the following 7 domains:

Power of Attention
Continuity of Attention
Cognitive Reaction Time
Response Variability
Quality of Working Memory
Quality of Episodic Secondary Memory
Speed of Memory

- MMRM on observed data
- Wilcoxon Rank test on observed data
- Change from Baseline in COWAT total score at Week 24

- MMRM on observed data
- Wilcoxon Rank test on observed data
- Change from Baseline in a composite z-score of the 7 CDR System domains plus the COWAT total score at Week 24
  - MMRM on observed data
  - Wilcoxon Rank test on observed data
- Change from Baseline in the sum of Parts A and B (Delusions and Hallucinations), and the sum of Parts of D and E (Depression and Anxiety) of the NPI at Week 24
  - MMRM on observed data
  - Wilcoxon Rank test on observed data
- Change from Baseline on the total severity score and distress score of the NEVHI score at Week 24 for subjects with visual hallucinations
  - MMRM on observed data
  - Wilcoxon Rank test on observed data
- Number (%) of patients with shifts from baseline in the NEVHI Total Severity Score and in the Distress Score (ie, 2 separate analyses) at Week 24, using a CMH row means score (CHM RMS) test. The categories for shifts are ordered as:
  - worsening from baseline
  - remaining unchanged from baseline
  - improving from baseline.

*Sample* SAS code for the CMH RMS is as follows (where MMSEbase is the baseline randomization stratum level for the patient, NOT the actual MMSE value):

```
Proc freq data=dat;  

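### The printed CDR composite formula leaves the z-score label off Cognitive Reaction Time, so a literal program would subtract milliseconds and one domain would dominate the composite.

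*Protocol*

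**What the plan says.** Protocol 8.3.1.5 builds the composite in three steps.

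- Table 4 defines the seven domain scores. Cognitive Reaction Time (COGRT) is the median choice reaction time minus the median simple reaction time, in ms.
- Next, "a standardized z-score will be derived for each CDR system domain using the formula below": (X2 - X1)/SD1. X2 is a post-baseline score, X1 is the subject's own baseline score, and SD1 "is the domain standard deviation of the population at Baseline".
- The domains are then combined with signs and divided by 7. The formula closes with "Power of Attention z-score - Cognitive Reaction Time - Speed of Memory z-score)/7". The other six terms carry the z-score label; COGRT does not.

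SAP 5.13 repeats the definitions and the formula below Table 13, with the same omission. Its lead-in reads "A composite z-score for the 7 CDR domains will be calculated based on the individual domain scores as", which refers to domain scores rather than domain z-scores. The SAP adds a missing-data rule: when one domain is absent, "the average of the 6 non-missing Domain z-scores will be used to replace the missing Domain z-score".

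Two tertiary endpoints name a CDR composite (Protocol section 4): "Change from Baseline in the composite z-score combining the 7 domains of the CDR computerized assessment system at Week 24" and "Change from Baseline in composite z-score combining the 7 CDR System domains plus the COWAT at Week 24". SAP 9.4.2 analyses both by MMRM and Wilcoxon test. SAP 7.3 gives the SAP precedence where the documents differ. That does not help here, because they agree.

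**The concern.** Six terms are unit-free changes of order 1. The seventh, as printed, is a time in milliseconds. Dividing the sum by 7 gives equal weights only if all seven terms are on the same scale.

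A programmer who codes the formula as it stands gets a variable that is called a seven-domain cognition score but mostly follows one reaction-time difference. Working memory, episodic memory and continuity of attention would hardly register. The lead-in does not rule this reading out, since it refers to domain scores. At stake is the validity of the tertiary seven-domain composite, and possibly of the CDR+COWAT composite.

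**Working it through.** **No stated figure to reproduce.** Neither document gives an SD, variance or power for the CDR composite.

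**Inputs from the documents.** Seven equally weighted terms; six z-scored; COGRT in ms; divisor 7.

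**Assumptions, not in the documents.**

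- Each of the six z-scores has variance 1. Each is a change divided by the baseline SD. If the spread is stable over time, its variance is 2(1 - c), where c is the baseline to Week 24 correlation. This equals 1 at c = 0.5.
- The SD of the raw COGRT term, s, is 30, 50, 100 or 200 ms.
- A common correlation r, after aligning signs, holds between all seven domains, COGRT included: 0 or 0.3.

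**Formula.** Before division by 7:

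- variance of the six z-scores together = 6 + 30r
- covariance terms between COGRT and those six = 12rs
- total = s² + 6 + 30r + 12rs
- COGRT own-variance share = s² / total
- COGRT share including half of its covariance terms = (s² + 6rs) / total

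**Results as printed.**

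| s (ms) | Own share, r = 0 | Own share, r = 0.3 | Share with covariance, r = 0.3 |
|---|---|---|---|
| 30 | 900/906 = 99.3% | 900/1,023 = 88.0% | 954/1,023 = 93.3% |
| 50 | 2,500/2,506 = 99.8% | 2,500/2,695 = 92.8% | 2,590/2,695 = 96.1% |
| 100 | 10,000/10,006 = 99.94% | 10,000/10,375 = 96.4% | 10,180/10,375 = 98.1% |
| 200 | 40,000/40,006 = 99.99% | 40,000/40,735 = 98.2% | 40,360/40,735 = 99.1% |

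In the least extreme cell (30 ms, r = 0.3), the squared correlation between COGRT and the composite is 954²/(900 × 1,023) = 0.989.

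**Results as intended.** With seven unit-variance z-scores, each domain's share including covariance is 1/7 = 14.3% at any common r. The own-variance share is 1/7 at r = 0 and 1/(7 + 42 × 0.3) = 1/19.6 = 5.1% at r = 0.3.

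**Scale of the composite.** At r = 0 and s = 50 ms, the printed formula gives an SD of √2,506/7 = 7.15. The intended formula gives √7/7 = 0.38.

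**How small must s be?** At r = 0 the own share falls below 90% when s² < 54, that is s below about 7.3 ms. At r = 0.3 it does so when 0.1s² - 3.24s - 13.5 < 0, that is s below about 36 ms. Beyond the main range, at r = 0.5 and s = 50 ms, the own share is 2,500/(2,500 + 21 + 300) = 88.6% and the share with covariance is 2,650/2,821 = 93.9%.

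**The case against.** The strongest reply is that the context already settles the meaning. A z-score is derived for every domain, the result is named a composite z-score, and the SAP's missing-domain rule makes sense only if all seven components are z-scores. The formula itself mentions no unit and no raw value. This stands as evidence of intent, and a reader who inferred that the sponsor means to subtract raw milliseconds would go too far. It does not repair the formula. The derivation is printed the same way twice and correctly nowhere, and a prespecified score should not depend on a programmer's silent correction.

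Three other inferences are tempting, and the documents do not support them.

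- **A share of 98% or more in every case.** That requires zero correlation between COGRT and the other six domains. Nothing in the documents supports zero: Power of Attention is SRTM+VIGRT+CRTM, so it contains both components of COGRT. With a correlation of 0.3 the own share starts at 88%.
- **The composite would use the level of COGRT, not its change.** The endpoint is a change from baseline in the composite. If the formula is also evaluated at baseline, differencing leaves a change in COGRT. The documents define the z-scores only post-baseline and do not settle this.
- **The CDR+COWAT composite has the same fault.** Its endpoint is described as "Change from Baseline in a composite z-score of the 7 CDR System domains plus the COWAT total score at Week 24", but no formula is given. It may be built from the seven-domain composite or from separate domain z-scores.

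**Conclusion.** The formula in Protocol 8.3.1.5 and SAP 5.13 is wrong as printed and contradicts the text around it. It is an omission in the specification, most likely a dropped label.

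If it were programmed literally, COGRT would dominate: about 88% to over 99.9% of the composite's variance on the own-variance measure, against about 1/7 as intended. Those percentages rest on assumed SDs of 30 to 200 ms, unit-variance z-scores and a common correlation of 0 to 0.3. The exact share is therefore uncertain. The dominance is not, unless the SD is far smaller than assumed.

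The reach is limited. The seven-domain composite is affected directly, and the CDR+COWAT composite only if it uses the same formula. Both are tertiary. The primary and secondary endpoints, the sample size and the alpha rules are untouched. The individual domains are analysed on their actual scores (SAP 9.4.2) and do not use this formula. The point is worth correcting before programming and unblinding, but it does not threaten the trial's main conclusions.

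**What to change.** - In Protocol 8.3.1.5 and SAP 5.13, change the term to *- Cognitive Reaction Time z-score*.
- In the lead-in sentence of both sections, write *individual domain z-scores* in place of the reference to domain scores.
- If the CDR+COWAT composite is built from the seven-domain composite, use the corrected version there.

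The cost is a few words in each document, with no new data and no change to the analyses. The correction should be recorded before unblinding, since the SAP introduction says that all analysis decisions precede it.

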#### **8.3.1.6. Controlled Oral Word Association Test (COWAT)**

The COWAT, which is subtest of the Multilingual Aphasia Examination ([Benton, 1994](#)), is a verbal fluency test that measures spontaneous production of words beginning with some designated letter. The COWAT uses the three letter set to assess phonemic fluency. Individuals are given 1 minute to name as many words as possible beginning with one of the letters. The procedure is then repeated for the remaining two letters. The COWAT takes approximately 5 to 10 minutes to administer. This scale will be administered by a rater who is trained for this study.

#### **8.3.1.7. Alzheimer's Disease Cooperative Study - Activities of Daily Living (ADCS-ADL)**

The ADCS-ADL scale ([Galasko et al., 1997](#)) measures functional impairment in terms of activities of daily living. The ADCS-ADL is an interviewer-administered, informant-based scale where the informant (caregiver) responds to 23 activities of daily living questions about the subject. The questions range from basic to instrumental activities of daily living and take approximately 20 minutes to complete. The total score ranges from 0 to 78; the lower the score, the greater the impairment. This scale will be administered by a rater who is trained and certified for this study.

#### **8.3.1.8. Clinician Assessment of Fluctuation (CAF)**

The CAF assesses fluctuating cognition and impaired consciousness over the previous month ([Walker, 2000](#)). The CAF is one of the measures of cognitive fluctuation recommended by the DLB Consortium when applying the DLB diagnostic criteria ([McKeith et al., 2005](#)). The CAF is a 2-item questionnaire, with the first item capturing the presence of fluctuating level of consciousness and the second item capturing the presence of fluctuating cognitive impairment. According to the CAF, fluctuating cognition is considered present if either of the scale's 2 items is marked 'yes'. In addition, if fluctuating cognition is present, frequency and duration are assessed each on a separate scale. These 2 values (frequency and duration) are multiplied to

achieve a severity score (Van Dyk et al., 2015). This scale will be administered by a rater who is trained for this study.

#### **8.3.1.9. North East Visual Hallucinations Inventory (NEVHI)**

The NEVHI is a semi-structured interview that assesses visual hallucinations in elderly patients with visual and/or cognitive impairments (Mosimann, 2008). The NEVHI has 3 sections. It will take approximately 3 minutes for subjects without visual symptoms and up to 12 minutes for subjects with hallucinations. Section 1 screens for the presence of visual hallucinations and assesses hallucination phenomenology. Section 2 assesses the severity of hallucinations by rating temporal aspects (frequency and duration) of hallucinations. Section 3 assesses emotion, cognition, and behavior associated with the most prominent recurrent visual hallucination during the month prior to the assessment. This scale will be administered by a rater who is trained for this study.

#### **8.3.1.10. Neuropsychiatric Inventory**

The full NPI (Cummings et al., 1994) is a 12-item behavior rating scale composed of a structured interview of the caregiver, which assess psychiatric disturbance. In this study, only Parts A, B, D & E of the NPI will be performed, which assess delusions hallucinations, depression/dysphoria and anxiety, respectively. Both the frequency and the severity of each behavior are determined. Two separate 2-item subscores will be calculated; one for Parts A and B (delusions and hallucinations domains) and one for Parts D & E (depression and anxiety domains) of the NPI. This scale will be administered by a rater who is trained for this study.

#### **8.3.1.11. EuroQol Five Dimensions Questionnaire, Five Level Version (EQ-5D-5L)**

The EQ-5D-5L is a standardized measure of health status that provides a measure of health-related quality of life that is widely used in clinical trials (Rabin, 2001). For this study, the EQ-5D-5L will be a caregiver proxy assessment. The assessment will be completed by the caregiver and will assess the caregiver's impressions of how the subject would rate his/her own quality of life. The EQ-5D-5L questionnaire consists of 2 components: the EQ-5D-5L descriptive system and the EQ visual analogue scale (EQ VAS). The EQ-5D-5L descriptive system includes 5 dimensions: mobility, self-care, usual activities, pain/discomfort, and anxiety/depression. The EQ VAS records overall health status on a 20-cm vertical line with a score of 0 (worst health one can imagine) to 100 (best health one can imagine). This scale will be administered by a rater who is trained for this study.

#### **8.3.1.12. Dependence Scale (DS)**

The DS measures the amount of assistance patients with dementia require in performing daily activities (Brickman et al., 2002). The caregiver answers questions about the dependency of the subject. The scale consists of 13 items, representing a range of severity from mild to severe levels of dependency. The score range is from 0 to 15 with higher scores indicating greater dependency. This scale will be administered by a rater who is trained for this study.

